**B-Lay Summary Research Design**

**Describe the purpose of this study in lay terms, including research question(s) and hypothesis.**

The purpose of this-group, randomized, controlled trial is to evaluate the refined SystemCHANGE™ against attention control patient education in CKD patients taking RAAS medications. Patients will be recruited from two sources: 1) the largest and most comprehensive health care system in the state and 2) one of the largest essential health care systems in the country. Data are collected at baseline, 8 weeks(immediately post-intervention)and 12 weeks. Specific aims are to: Aim 1. Estimate acceptability, outcome expectancy and credibility of the refined SystemCHANGE™ Intervention and for the attention control at 8 and 12 weeks after baseline. Aim 2. Estimate preliminary efficacy of SystemCHANGE™ Intervention versus attention control on medication adherence (primary outcome) and personal systems behavior (mechanism of action) at 8 and 12 weeks among people with CKD taking a once-daily RAAS inhibiting medication. The immediate impact of this study will be data to inform the design of a future, fully powered, efficacy trial. If findings are as expected, we will proceed to an R01 application. If findings are not as expected (e.g., negative), we will work to improve the SystemCHANGE™ intervention or move to a different intervention in future trials. The long-term impact of this line of research will be additional empirical evidence for novel medication adherence interventions in this population to inform future evidence-based guidelines, position statements, and practice recommendations.

**List and describe all research interactions and/or interventions, including the frequency and duration of procedures, and length of participation for individual subjects.**

WHAT WILL HAPPEN DURING THE STUDY? This study has 3 phases- the screening phase, the intervention phase, and the maintenance phase. Before being invited to participate in this study, you will be asked questions from the 6-item cognitive screening survey to make sure you qualify for the study.

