**State the potential benefits or information which may accrue to SCIENCE or SOCIETY in general as a result of this work.**

The immediate impact of this study will be data to inform the design of a future, fully powered, efficacy trial. If findings are as expected, we will proceed to an R01 application. If findings are not as expected (e.g., negative), we will work to improve the SystemCHANGE™ intervention or move to a different intervention in future trials. The long-term impact of this line of research will be additional empirical evidence for novel medication adherence interventions in this population to inform future evidence-based guidelines, position statements, and practice recommendations.

---

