### **Statistical Design and Power.**

**A.1. Statistical Design.** This two-arm randomized single masked experimental design pilot study compares SystemCHANGE™ with attention control patient education using repeated measures in adults with CKD and poor adherence to prescribed RAAS inhibitor medication. Randomization will be stratified by *moderate* (.70 - .84) and *low* (<.70) *medication adherence*.

**A.2. Sample Size Justification and Power Analysis.** Sample size is based on considerations for designing pilot studies and based on this study's aims. Hertzog suggests 30 participants per group is sufficient for estimating preliminary efficacy. Based on these practical considerations and anticipated attrition based on our prior studies, we will enroll 66 individuals, to retain 60 with CKD stage 1-4 and poor adherence. The resulting 30 participants per group will be sufficient for estimating preliminary efficacy. Statistical analyses will be conducted to determine acceptability, outcome expectancy and credibility (Aim 1) and to calculate preliminary effect size estimates (Aim 2) that may be used in combination with other evidence to justify a future randomized trial; however, efficacy estimates themselves will not solely be used to determine the sample size for the larger study (Leon AC, Davis LL, Kraemer HC. The Role and Interpretation of Pilot Studies in Clinical Research. *J Psychiatr Res* 2011 May; 45(5): 626-629; doi:10.1016/j.jpsychires.2010.10.008).

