**A.3. Analytic Plan.** We will conduct rudimentary analyses to ensure that data have been properly collected and to identify outliers or errors. Data manipulation and analysis will be conducted in SAS Version 9.4 (SAS Institute Inc., Cary, N.C.) and all syntax documented to ensure reproducibility. We will calculate the proportion eligible that enroll and complete the intervention. Aim 1: We will tabulate responses to acceptability, outcome expectancy and credibility items. Aim 2: Effect sizes will be estimated by fitting ANCOVA models with treatment group as the explanatory variable and outcomes: 1) adherence and 2) personal systems behavior. Effects sizes will be estimated with  $\omega^2$ . Analyses will be intent-to-treat. Supplementary analyses will investigate how the adjustment for levels of the covariate (e.g. male and female for sex) impacts effect size estimates by adding interaction terms to models and estimating effect sizes separately for the different levels. **Missing Data:** We will compare baseline variables between subjects who drop out of the study to those who do not using two-sample *t* tests, chi-square tests or non-parametric equivalents as appropriate. If we find that missing data appear to be not missing at random, this information will be used in designing the larger trial. Due to the relatively small sample size, we will not attempt to model the missing data mechanism in this pilot study. **Sex as a biological variable:** As noted above, we will estimate effect sizes by sex for all outcomes. Additionally, for Aim 1, qualitative interviews will be recorded, transcribed verbatim, and entered into the NVivo 12 (QSR Int.) qualitative software. We will use standard content analysis procedures to code data into meaningful categories regarding acceptability. The resulting qualitative data will be combined with quantitative data in side-by-side summary tables to derive integrative summary statements to draw conclusions about participant acceptability.

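### The only effect measure named for Aim 2 is ω², which carries no direction; the plan commits to no signed adjusted difference and no confidence interval, overall or by sex

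*SAP*

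**What the plan says.** SAP section A.3 (Analytic Plan) sets the Aim 2 model: "Effect sizes will be estimated by fitting ANCOVA models with treatment group as the explanatory variable and outcomes: 1) adherence and 2) personal systems behavior". It continues: "Effects sizes will be estimated with" ω². No other Aim 2 measure appears.

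The supplementary analyses look at covariate levels by "adding interaction terms to models and estimating effect sizes separately for the different levels", and the paragraph on sex adds that "we will estimate effect sizes by sex for all outcomes". Neither names a different measure or an interval.

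Nowhere does the SAP mention an adjusted mean difference, least-squares means, a model coefficient, a standardized difference, a standard error or a confidence interval. The Protocol (B-Lay Summary Research Design) states Aim 2 as preliminary efficacy against attention control on "medication adherence (primary outcome) and personal systems behavior (mechanism of action) at 8 and 12 weeks", again without an effect measure.

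On use of the results, SAP section A.2 says the study is to "to calculate preliminary effect size estimates (Aim 2) that may be used in combination with other evidence to justify a future randomized trial". The Protocol (sections B and E) plans a larger grant application if results come out as hoped, and otherwise says: "If findings are not as expected (e.g., negative), we will work to improve the SystemCHANGE™ intervention", or a move to a different intervention.

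**The concern.** Aim 2 is an estimation aim. Its reader needs to know which arm did better, by how much, and how uncertain that is. The one measure the plan names gives a share of variance explained. It has the same value whether SystemCHANGE helped or harmed by a given amount, and the plan attaches no interval to it.

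The by-sex analysis is affected more. The interaction terms could show that the sexes differ, but neither ω² for the interaction nor ω² within each sex shows which sex benefits. Similar values in men and women could be read as similar effects when the effects point in opposite directions.

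The Protocol makes the next step depend on whether findings are as expected or negative, so direction matters to the study's own decision. If the signed estimate is not fixed in advance, the headline summary can also be chosen after the data are seen.

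**Working it through.** **Inputs from the documents.** SAP A.2: 66 enrolled, 60 retained, 30 per group. SAP A.3: ANCOVA, ω² as effect size, effect sizes by sex.

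**Inputs assumed.** The documents give no target effect, covariate–outcome correlation r or sex split. Values for these are illustrative, and effects are in SD units.

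**The plan's own figure.** 2 × 30 = 60. Enrolling 66 to retain 60 implies 6/66 = 9.1% attrition. This is internally consistent, and the point here does not depend on it. The plan states no expected ω² or interval width to reproduce.

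**Step 1: direction.** For a one-degree-of-freedom contrast with n per arm and N = 2n:

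- t = d × √(n/2), F = t²
- ω² = (F − 1)/(F − 1 + N)

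| Observed d (30 per arm) | F | ω² |
|---|---|---|
| +0.5 or −0.5 | 0.25 × 15 = 3.75 | 2.75/62.75 = 0.044 |
| +0.3 or −0.3 | 0.09 × 15 = 1.35 | 0.35/60.35 = 0.006 |
| +0.1 or −0.1 | 0.01 × 15 = 0.15 | −0.85/59.15 = −0.014 |

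The estimate can fall below zero when F < 1. That is the bias correction at work and does not signal harm: +0.1 and −0.1 give the same negative value.

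The same holds in an adjusted model. In one simulated ANCOVA data set of 60, swapping the arm labels moved the adjusted difference from +0.57 (95% CI 0.19 to 0.95) to −0.57 (−0.95 to −0.19). ω² stayed at 0.098 (total-sum-of-squares form) or 0.120 (partial form).

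**Step 2: overall precision.** At d = +0.5 and 30 per arm, inverting the noncentral t (58 df) gives a 95% CI of −0.016 to 1.012, mirrored for −0.5. The half-width of the interval for the difference is t(0.975, df) × √(2/n) × √(1 − r²):

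- r = 0, 58 df: 0.517
- r = 0.3, 57 df: 0.493
- r = 0.7, 57 df: 0.369

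An interval for ω² itself would also be wide: at d = ±0.5, the noncentral-F interval is about 0 to 0.20 with 60 participants.

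**Step 3: within one sex (separate unadjusted models).**

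- 15 per arm (even split assumed), d = ±0.5: F = 0.25 × 7.5 = 1.875; ω² = 0.875/30.875 = 0.028 for both signs; half-width t(0.975, 28) × √(2/15) = 0.748.
- 9 per arm (a sex making up 30% of the sample): half-width t(0.975, 16) × √(2/9) = 0.999.

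**Step 4: sex-by-treatment interaction.** Take 15 per arm per sex, with d = +0.5 in one sex and −0.5 in the other:

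- contrast = 1.0; SE = √(4/15) = 0.516; t = 1.94; F = 3.75
- 95% CI (56 df, half-width 1.034): −0.034 to 2.034
- partial ω² = 2.75/62.75 = 0.044

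Reversing which sex benefits flips the sign of the contrast and leaves F and ω² unchanged.

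**The case against.** ω² is a legitimate effect size for an ANCOVA. No planned estimate is biased, and the fitted model yields the coefficient and its standard error, so the team can read the sign whenever it wishes. For a one-degree-of-freedom contrast, ω² and N even give back F: 60 × 0.0438/(1 − 0.0438) + 1 ≈ 3.75, so |t| ≈ 1.94. In the unadjusted case the interval width then follows too. The Protocol's word for an unwelcome result may mean no effect, which a near-zero ω² would show. There is no numeric decision rule, and SAP A.2 uses the estimates only alongside other evidence. The effect sizes and sex split above are assumed. The Protocol's amendment form also reports the study closed to enrollment with numbers short of what a complete analysis needs, so the planned 30 per arm may not be the real figure.

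Much of this stands, and it limits the consequence to moderate. It does not remove the point. Working back from ω² recovers |t| but never the sign, and with covariates the raw difference also needs the residual SD. An interval that a reader must reconstruct is not a reported interval. A null result and a harmful one may both count as negative, but a harmful effect of some size gives the same ω² as a beneficial one. If fewer than 30 per arm are analysed, the intervals will, other things equal, be wider than shown, which strengthens the case for reporting them.

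**Conclusion.** The concern holds. The plan names ω² as its sole Aim 2 effect measure and commits to no signed adjusted difference and no confidence interval, for either outcome, at either time point, overall or by sex.

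That ω² is blind to direction is an algebraic fact and rests on no assumption. The sizes are illustrative at the planned sample. Differences of +0.5 and −0.5 SD share ω² = 0.044 while their intervals lie on largely opposite sides of zero. Half-widths run from about 0.37 to 0.52 SD overall (r from 0.7 down to 0), about 0.75 to 1.00 SD within one sex, and about 1.03 SD for the interaction contrast.

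This is a gap in committed reporting, not an error in the model. It should be corrected because estimating efficacy is what Aim 2 is for, and the study's next step turns on direction.

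**What to change.** In SAP section A.3, make the primary Aim 2 estimate the ANCOVA-adjusted mean difference, SystemCHANGE minus attention control, with its 95% confidence interval. State it for adherence and for personal systems behavior, at 8 weeks and at 12 weeks. A.3 does not name the time points, so a clause taking them from the Protocol's Aim 2 is needed. Report the difference within each sex and the sex-by-treatment interaction contrast the same way, each with a 95% interval. Keep ω² as a supplementary measure.

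The cost is a few sentences and some output lines from the ANCOVA and interaction models already planned. Data collection and sample size do not change. Because enrollment has closed, date the change and record whether outcome data had been examined by arm. The one drawback is that the intervals will look wide, especially by sex and for the interaction; that is an accurate picture of what about 60 participants can show.

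### The by-sex analysis in SAP A.3 asks about adjustment, fits an interaction, and names only an unsigned effect size per sex; the treatment-by-sex contrast and its interval should be the named result

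*SAP*

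**What the plan says.** SAP A.3 estimates the Aim 2 effects on adherence and personal systems behavior by ANCOVA, with omega-squared as the effect size. A supplementary analysis then looks at the influence of covariate levels, with sex as the example, "by adding interaction terms to models and estimating effect sizes separately for the different levels". The paragraph on sex as a biological variable restates the output: "we will estimate effect sizes by sex for all outcomes".

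A.3 names no interaction estimate, no confidence interval for a sex difference, and no guidance on reading two sex-specific values side by side.

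On size, A.2 states "we will enroll 66 individuals, to retain 60 with CKD stage 1-4 and poor adherence" and concludes "The resulting 30 participants per group will be sufficient for estimating preliminary efficacy". Neither document gives an expected sex split. A.1 stratifies randomization by adherence level only, so balance between arms within each sex is left to chance.

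**The concern.** Two questions are run together. Adjustment asks how the treatment estimate changes when sex enters as a main effect. Effect modification asks whether the treatment effect differs between the sexes, and needs the treatment-by-sex term. The SAP's sentence states the first aim and prescribes the second method, so the adjustment question is left unanswered.

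For effect modification, the quantity of interest is the difference between the two sex-specific treatment differences. The model that A.3 already fits yields it, but A.3 does not name it as a result. A report that followed the text literally would show two omega-squared values per outcome. Omega-squared measures variance explained, so a benefit in one sex and an equally large harm in the other would give the same value. Without a signed contrast and an interval, a reader cannot tell a chance gap from a real one.

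What is at stake is how the pilot is read. Its purpose is to inform a larger trial, and by-sex values are promised for every outcome.

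**Working it through.** **Inputs**
- Retained: 60, or 30 per arm (SAP A.2). A.2 rests on a pilot-study rule and states no alpha, power, effect or SD, so there is no power figure to reproduce. Going from 66 to 60 implies 1 − 60/66 = 9.1% attrition; no rate is stated.
- Sex split: not given. Assumed 50:50, so n = 15 per arm per sex. Range: 40:60 (12 and 18 per arm) and 30:70 (9 and 21 per arm). At 60 retained, the smaller sex averages at most 15 per arm.
- True effect: 0.5 SD in both sexes (assumed), so there is no real sex difference.
- Outcome SD set to 1. The SAP names no baseline covariate; correlations of 0, 0.5 and 0.7 with outcome are assumed.

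**1. Precision of the sex difference**

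SE within one sex = √(2/n) = √(2/15) = 0.365.

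SE of the interaction contrast = √(2/15 + 2/15) = √(4/15) = 0.516.

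95% half-width with four cells of 15 (56 df, t = 2.003): 2.003 × 0.516 = 1.03 SD.

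A baseline covariate with correlation ρ multiplies this by √(1 − ρ²):
- ρ = 0.5: 1.03 × 0.866 ≈ 0.90 SD
- ρ = 0.7: 1.03 × 0.714 ≈ 0.74 SD

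The split matters less. With normal quantiles and no covariate, the half-width is 1.01 SD at 50:50, 1.03 at 40:60 and 1.10 at 30:70. For comparison, the whole-arm half-width is 1.96 × √(2/30) = 0.51 SD.

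**2. How often the two estimates point in opposite directions**

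P(one sex's estimate is below zero) = Φ(−0.5/0.365) = Φ(−1.37) = 0.085.

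P(opposite signs) = 2 × 0.085 × 0.915 = 0.156, about 16%.

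With a covariate the SE within a sex falls to 0.365 × 0.866 = 0.316 or 0.365 × 0.714 = 0.261:
- ρ = 0.5: Φ(−0.5/0.316) = 0.057, giving 2 × 0.057 × 0.943 = 11%
- ρ = 0.7: Φ(−0.5/0.261) = 0.028, giving 2 × 0.028 × 0.972 = 5%

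Omega-squared shows none of these reversals.

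**3. How often the two omega-squared values differ**

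The population value for two equal groups is d²/(d² + 4) = 0.25/4.25 = 0.059. The sample value is (SSB − MSW)/(SST + MSW), which for two groups of n equals (t² − 1)/(t² − 1 + 2n).

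Simulated trials with 15 per arm per sex, no covariate and the same true effect in both sexes gave:

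| Event | Share of trials |
|---|---|
| The two values differ by more than 0.06 | about 55% |
| One sex at or above 0.06, the other at or below 0.01 | 30% |
| A given sex's value is negative | about 34% |

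A gap larger than the true value itself therefore occurs in more than half of trials with no sex difference. With 12 per arm in each sex, the first figure is about 58%. With a true effect of zero in both sexes and 15 per arm, a gap of at least 0.06 occurs in 25%.

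**4. What naming the contrast can and cannot do**

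At 15 per arm per sex without a covariate, power for a true sex difference of 0.5 SD is 16%, and 80% power needs about (1.96 + 0.84) × 0.516 = 1.45 SD. Reporting the contrast does not remove the noise; it makes the noise visible.

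**The case against.** The strongest reply is that this is a supplementary analysis in a pilot. A.2 describes the efficacy estimates as preliminary, to be combined with other evidence, and says they alone will not size the next trial. No document plans a sex-difference claim or a decision based on one. All of that stands, and it keeps the point minor.

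The SAP also does fit interaction terms, so it cannot be said to ignore interaction, and a short plan need not list every output. This stands too. The narrower point remains: the only output named is a per-sex effect size, and its metric is unsigned.

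The calculations use a simpler model than the planned ANCOVA. A prognostic covariate would narrow the interval and reduce sign reversals, as the ranges above show. It would not rescue omega-squared: if that is computed on the covariate-adjusted residual, the same benefit becomes a larger standardized effect, and gaps need not become rarer.

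A reader might infer two stronger points that the documents do not support:
- *The SAP breaches its own size standard.* A.2 says its source "suggests 30 participants per group is sufficient for estimating preliminary efficacy", and it applies that figure to the randomized arms. It never says the sex-specific estimates meet it.
- *Unequal SDs will distort the comparison between sexes.* That requires each sex's omega-squared to use that sex's own variance. The SAP does not specify this, and its interaction-model wording fits a common residual variance equally well.

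**Conclusion.** The point holds as a minor one about specification and reporting. A.3 poses an adjustment question and answers it with an interaction model. It then names only an unsigned effect size per sex and leaves out the contrast that would answer the effect-modification question.

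On an even split (assumed) and an identical true effect of 0.5 SD (assumed), the planned output would differ by more than 0.06 between the sexes in about 55% of trials, and would hide opposite-signed estimates in about 16% (5% to 11% with the assumed covariate). The interval for the sex difference has a half-width of about 1.03 SD without a covariate and about 0.90 to 0.74 SD with one.

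The conflation of adjustment with effect modification, and the missing contrast, follow from the text and need no assumption. The primary Aim 2 estimate is unaffected.

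**What to change.** Replace the supplementary-analysis sentence in A.3 with two steps.

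(a) *Adjustment.* Refit the Aim 2 model with sex as a main effect only, and report how the adjusted treatment difference changes.

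(b) *Effect modification.* Fit one model with treatment, sex and their interaction, and a common residual variance. Report the two sex-specific adjusted treatment differences in outcome units and the difference between them (the interaction), each with a 95% CI. Give the number per sex and arm, and label the by-sex results descriptive.

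A rule that a sex difference may inform the next application only if the interval excludes zero is not recommended. With 16% power for a 0.5 SD difference, it would discard most real signals and would put a significance gate on an estimation pilot.

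The cost is a few lines of SAP text and one extra contrast from a model already being fitted. The downside is that the by-sex result will visibly be imprecise.

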virtually. Before that meeting, your electronic cap, and the bottle will be returned to you and you will be asked to use it for 12 more weeks. You will also be asked to complete additional surveys. These surveys include 1) Acceptability Scale, 2) Outcome Expectancy, 3) Treatment Credibility Questionnaire. You will again use a special bottle and cap to keep and take your medication. You will also be given a special mobile phone for this study. Each week for 6 weeks, you will place the phone near the bottle to send data to the study team. After the data is received, you will get one text message on the provided mobile phone each week for 6 weeks. These text messages are education about your disease and disease process. A member of our study team will call you each week to ask you questions and make sure the equipment is working correctly. The study team member will also discuss information from the first visit with you. We will also ask you about any healthcare visits that you have with your healthcare provider. This might include a visit to your providers for a checkup and any time spent in the hospital or a visit to the emergency room. Treatment group 1 will receive education that will help to learn more about caring for your chronic kidney disease. You will receive your first materials during the research nurse's visit to your home. You will receive a telephone call from the research nurse to review and discuss the educational materials throughout the study. In addition, the research nurse will ask you if you have had any changes to your medications and what healthcare providers you have seen recently. Treatment group 2 will receive training by a research nurse who will work with you to learn about SystemCHANGE™. You will get a printer report from the MEMS cap to see how you are doing with taking your medications. Part of this intervention involves completing time worksheets together with the study nurse (Important People Form, Life Routine Form, Solutions Form). This helps you identify people who are important in helping you with taking your medicines, and identify your daily routines, specifically the routines around the times that you are scheduled to take your medicines. The research nurse will ask you to think about possible changes in your routines that may make it easier for you to take your medicines every day on time without having to remember. The research nurse will call you to discuss the important people you marked on the Important People Form and which solutions you have decided to use from the Solution Form. Throughout the study, the research nurse will send your personal medication-taking report. The research nurse will then telephone you to discuss how you are doing with taking your medicine every day on time using the forms. Together, you will discuss

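### Aim 2 is labelled intent-to-treat, but the SAP gives its ANCOVA no method for randomised participants whose 8- or 12-week outcome is missing

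*SAP*

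**What the plan says.** SAP A.3 sets the principle: "Analyses will be intent-to-treat". It then sets the method: "Effect sizes will be estimated by fitting ANCOVA models with treatment group as the explanatory variable", with adherence and personal systems behavior as outcomes and omega-squared as the effect measure. The outcome times, 8 and 12 weeks, come from the Protocol's lay summary (Aim 2).

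The SAP's missing-data paragraph has three parts. The first is a descriptive check: "We will compare baseline variables between subjects who drop out of the study to those who do not". The second is what happens if that check suggests trouble: "this information will be used in designing the larger trial". The third is a limit: "Due to the relatively small sample size, we will not attempt to model the missing data mechanism in this pilot study". There is no imputation, no likelihood-based repeated-measures model, no rule for scoring a partly observed period and no sensitivity analysis.

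On numbers, SAP A.2 says "we will enroll 66 individuals, to retain 60 with CKD stage 1-4 and poor adherence", and then "The resulting 30 participants per group will be sufficient for estimating preliminary efficacy".

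On data, the Protocol's description of the intervention phase says "Each week for 6 weeks, you will place the phone near the bottle to send data to the study team". Cap use runs for 12 weeks, and the maintenance-phase text has the cap mailed back at the end.

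**The concern.** An intent-to-treat estimate compares everyone as randomised. An ANCOVA at 8 or 12 weeks can use only people who have a value at that time, and the plan does nothing for the rest. If those who leave would have adhered less than those who stay, the arm that loses more people looks better than it should, and the estimate still carries the intent-to-treat label.

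The reason given does not cover the gap. Few participants is a fair reason not to model why data are missing. It is not a reason to have no handling at all, because a mixed model fitted by likelihood is valid under missing at random without a model of the mechanism. SAP A.1 already describes the design as repeated measures, but A.3 does not say how the repeated measurements enter the analysis.

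The effect estimate is the main product of Aim 2, and the Protocol's lay summary makes the R01 application depend on whether findings are as expected. Unequal loss is plausible, since SystemCHANGE adds worksheets and routine-change work that the control arm does not have. Leaving the handling open also means it could be chosen after the data are seen.

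**Working it through.** **Inputs.** From SAP A.2: 66 enrolled, 60 retained, 30 per group. From the Protocol: outcomes at 8 and 12 weeks, uploads for 6 weeks, cap use for 12. Neither document gives an attrition rate, an SD, the timing of dropout or a difference between dropouts and completers. I take the 66 as randomised, 33 per arm, and treat the gap between dropouts and completers as an assumption ranging from 0.25 to 1.0 SD.

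**The plan's figure.** Implied loss is 6/66 = 9.1%, and 60/(1 − 0.0909) = 66. This is circular, because the rate is back-calculated. An assumed 10% gives 60/0.90 = 66.7, rounded up to 67, or 60 × 1.10 = 66. The target of 66 therefore fits attrition of roughly 9 to 10%.

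**Bias from analysing only those with an outcome.** If dropouts in both arms would score a gap of g SD below completers, each arm's completer mean exceeds its all-randomised mean by (share lost) × g. With a and b lost in the two arms, the bias in the difference is (a − b)/33 × g, in favour of the arm that loses more.

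| Split of 6 losses | (a − b)/33 | g = 0.25 SD | g = 1.0 SD |
|---|---|---|---|
| 3/3 | 0 | 0 | 0 |
| 4/2 | 0.061 | 0.015 | 0.061 |
| 5/1 | 0.121 | 0.030 | 0.121 |
| 6/0 | 0.182 | 0.045 | 0.182 |

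An even split is not a guarantee. If the gap exists in one arm only, a 3/3 split gives 3/33 × g = 0.023 to 0.091 SD. The bias is proportional to (a − b), so doubling the losses in the same ratio doubles each entry in the table.

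**Precision.** For an unadjusted standardised difference, the 95% half-width is 1.96 × √(2/n). At n = 30 per arm it is 0.506 SD; at n = 33 it is 0.483 SD. The ratio of standard errors is √(30/33) = 0.953. Bringing all 66 back would gain about 5% at best, and less in practice because dropouts contribute partial data. The issue is bias and labelling, not precision.

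**What data could fill the gap.** Scheduled uploads cover 6 of 8 weeks (75%) of the first outcome period and 6 of 12 weeks (50%) of the second. From week 7 on, adherence data depend on the cap being returned. Nothing in the documents says personal systems behavior comes from the uploads.

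**The case against.** The strongest reply is that this is an estimation pilot with about 9% expected loss. The SAP acknowledges missing data, plans a dropout comparison and explains its restraint. SAP A.2 also says the efficacy estimates will not alone determine the size of the larger study. Against a half-width of about 0.51 SD, a bias of 0 to 0.18 SD is small. All of this stands and limits the weight of the point. It does not supply the missing method.

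Four stronger readings are tempting, and the documents do not support them.

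- A reader might infer that the SAP plans to analyse only the 60 retained. Enrolling 66 to retain 60 is ordinary inflation for attrition and does not define the analysis set.
- A reader might infer that everyone who withdraws is certain to be dropped. The SAP never says complete-case and defines no adherence window, so a score over the available cap days is neither planned nor ruled out. Omission is the normal behaviour of an ANCOVA, not a stated rule.
- A reader might infer that weekly uploads exist right up to withdrawal, or that withdrawers usually leave several weeks of data. Uploads are described for 6 weeks only, and no timing of dropout is given.
- A reader might infer that a large bias is already present. That needs an extreme split of the losses together with a wide gap, and the documents give neither.

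**Conclusion.** The point holds as a gap between label and method. SAP A.3 promises intent-to-treat but gives its ANCOVA no way to keep randomised participants whose 8- or 12-week outcome is missing, and the small-sample remark does not justify that.

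With 6 of 66 lost and an assumed gap of 0.25 to 1.0 SD that is equal in both arms, the bias runs from 0 (3/3) to between 0.045 and 0.182 SD (6/0). It is modest unless losses are unbalanced or attrition exceeds the plan. The Protocol's amendment rationale says enrolment fell short of what complete analysis needs. If fewer than 33 per arm were randomised, each loss weighs more than shown here.

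The plan should be corrected before analysis, but the gap does not by itself invalidate the pilot.

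**What to change.** **Adherence.** Make the primary analysis a mixed model with randomised arm, time and arm-by-time, adjusted for baseline adherence. Use all available cap data from every randomised participant: the weekly uploads to week 6 plus data from returned caps to week 12. Uploads alone cannot give the 8- and 12-week differences. Define the adherence window and how a partly observed period is scored, then read the two arm differences from the model. State whether data collected before withdrawal are kept. Limit the data to the 12 randomised weeks, so that cap data from control participants who later take SystemCHANGE under the amendment stay out.

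**Personal systems behavior.** Use the same type of model on whichever scheduled assessments are available. The uploads do not help this outcome.

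**Sensitivity.** Keep the ANCOVA in completers, with omega-squared, labelled as a completer analysis. Add one run with unobserved adherence set to zero, described as a scenario. It is not a bound on the arm difference, because it changes both arms.

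**Timing.** The lay summary's aims place the post-intervention assessment at 8 weeks, while its maintenance-phase text repeats the surveys at 6 weeks. These must be reconciled before a missing 8-week outcome can be defined.

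**Cost.** SAP wording and some SAS programming, with no new study procedure. At this sample size a simple covariance structure is needed. Omega-squared does not come directly from a mixed model, so report a standardised mean difference beside it. The model removes bias only as far as missing at random holds, and a participant with no cap data after randomisation adds almost nothing to it.
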